7.3 Medical History

The conditions/diagnoses recorded in medical/surgery history eCRF will be coded using the most current version of the Medical Dictionary for Regulatory Activities (MedDRA). Medical/surgical history data will be summarized by primary MedDRA system organ class (SOC) and preferred term (PT) for each treatment group and overall subjects in the Safety Dataset. Subjects reporting more than one condition/diagnosis for a given PT will

be counted only once for that term. Subjects reporting more than one condition/diagnosis within an SOC will be counted only once for the SOC total. Subjects reporting more than one condition/diagnosis will be counted only once in the overall medical history total. The SOCs will be presented in alphabetical order and the PTs will be presented in alphabetical order within each SOC.

7.4 Prior and Concomitant Medications

Medications prescribed for the treatment of Parkinson's disease (anti-PD medications) will be identified by the investigator and will be entered into the database and summarized separately from other medications. All medications will be coded using the World Health Organization (WHO) dictionary and will be summarized by generic name.

Summaries of 3 categories of anti-PD medications (anti-PD motor symptom medications, anti-PD non-motor symptom medications, and anti-PD sleep medications) will be prepared for the Safety Dataset for the following periods:

- from V1 prior to Day 1
- during the 26-week randomized treatment period (start date before or on the last date of the 26-week treatment Period and end date on or after Day 1)

Each summary will include the number and percentage of subjects who took each specific medication, each incremental number of medications (1, 2, 3, 4, 5, and 6 or more) and each cumulative number of medications (1 or more, 2 or more, 3 or more, 4 or more, and 5 or more). For the summary of anti-PD motor symptom medications, the count will be for medications other than levodopa-carbidopa.

The following summaries of other medications will be prepared for the Safety Dataset.

- Other medications prior to treatment (start date before Day 1)
- Other medications during the 26-week randomized treatment period (start date before or on the last date of the 26-week randomized treatment period and end date on or after Day 1)

Each summary will include the number and percentage of subjects who took each specific medication and the number who took 1 or more medications.

8.0 Treatment Exposure and Compliance

Summaries of treatment exposure and compliance will be prepared for the Safety Dataset.

8.1 Duration of Treatment and PEG-J Exposure

During the 26-Week Randomized Treatment Period

The duration of study drug exposure for LCIG subjects and the duration of study participation for OMT subjects during the 26-week randomized Treatment Period will be summarized with descriptive statistics (number of subjects with non-missing data, mean, standard deviation, median, minimum and maximum). In the 26-week randomized treatment period, the duration of LCIG study drug exposure will be calculated for each subject as the date of the last dose of LCIG study drug during the randomized treatment period minus the date of the first dose of LCIG study drug plus 1. The duration of study participation for OMT subjects will be calculated for each subject as the date of the last visit during the 26-week randomized treatment period minus the date of randomization.

For subjects with a PEG-J tube removal after their last infusion of Study M12-927 study drug during the 26-Week Randomized Treatment Period, the duration of PEG-J exposure for each subject will be calculated as the date of their final PEG-J removal minus the date of their initial PEG-J placement + 1. For subjects without a PEG-J tube removal after their last infusion of study drug during the 26-Week Randomized Treatment Period, the duration of PEG-J exposure during the 26-Week Randomized Treatment Period for each subject will be calculated as the date of their final participation in Study M12-927 (last contact or visit date) during the 26-Week Randomized Treatment Period minus the date of their initial PEG-J placement + 1.

The number and percentage of subjects in each of the following exclusive duration categories will be summarized for LCIG infusion exposure in the LCIG group and study participation for the OMT group.

- 1 to 28 days (1 – 4 weeks)
- 29 to 56 days (5 – 8 weeks)
- 57 to 84 days (9 – 12 weeks)
- ≥ 85 days (≥ 13 weeks)

In addition, duration of exposure will be summarized with descriptive statistics (number of non-missing observations, mean, standard deviation, median, minimum and maximum duration and total subject-years) and by total subject-years. Total subject-years of OMT, LCIG exposure and PEG-J exposure will be calculated by summing the duration of exposure across the respective set of subjects and dividing this sum by 365.25 (1 year will be considered to be 365.25 days).

During the Extension Period

For LCIG subjects who continue LCIG exposure after the 26-week randomized treatment period, the continuing LCIG exposure will be calculated as the last day of LCIG study drug in Extension Period minus the date of the last dose of LCIG study drug during the 26-week randomized treatment period. The first and last treatment dates will be recorded on the Study Drug Administration eCRF.

For OMT subjects who continue into Extension Period, the duration of LCIG study drug exposure during Extension Period will be calculated for each subject as the date of the last dose of LCIG study drug minus the date of the first LCIG infusion plus 1.

For LCIG subjects who continue with a PEG-J tube after the 26-week randomized treatment period, and with a PEG-J tube removal after their last infusion of Study M12-927 study drug, the duration of PEG-J exposure for each subject will be calculated as the date of their final PEG-J removal minus the date of their final

participation in Study M12-927 (last contact or visit date) during the 26-Week Randomized Treatment Period + 1. For subjects without a PEG-J tube removal after their last infusion of study drug, the duration of PEG-J exposure for each subject will be calculated as the date of their final participation in Study M12-927 (last contact or visit date) minus the date of their final participation in Study M12-927 (last contact or visit date) during the 26-Week Randomized Treatment Period + 1.

For OMT subjects who continue into Extension Period and with a PEG-J tube removal after their last infusion of Study M12-927 study drug, the duration of PEG-J exposure for each subject will be calculated as the date of their final PEG-J removal minus the date of their initial PEG-J placement + 1. For OMT subjects who continue into Extension Period and without a PEG-J tube removal after their last infusion of study drug, the duration of PEG-J exposure for each subject will be calculated as the date of their final participation in Study M12-927 (last contact or visit date) minus the date of their initial PEG-J placement + 1.

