6.2 Definition of Study Epochs and LCIG Treatment Period Reference Variables

The following study epochs have been defined to track each subject's progression from screening through study completion or premature discontinuation.

Epoch Name	Epoch Description
Pre	OMT group: prior to and including the day of randomization. LCIG group: prior to the day of initial device (NJ or PEG-J) placement.
Device Before in Randomized Treatment Period (LCIG group only)	From the date of the first device (NJ or PEG-J) placement procedure up to, but not including, the date of the first LCIG infusion for subjects in the LCIG group during the 26-week randomized treatment period. This Epoch is missing for subjects whose infusion started the same day as initial device placement.
Open in Randomized Treatment Period	OMT group: from the day after randomization through the end of study (date of last visit) during the 26-week randomized treatment period. LCIG group: from the date of the first LCIG infusion through the date of the last LCIG infusion during the 26-week randomized treatment period.
Pre in Extension Period (OMT group entering Extension Period only)	From the day after the last visit during 26-week randomized treatment period up to, but not including date of the first device (NJ or PEG-J) placement.
Device Before in Extension Period (OMT group entering Extension Period only)	From the date of the first device (NJ or PEG-J) placement procedure up to, but not including, the date of the first LCIG infusion.
Open in Extension Period	For subjects in OMT group entering extension period: from the date of the first LCIG infusion through the date of the last LCIG infusion. For subjects in LCIG group entering extension period: from the date after the last LCIG infusion during the 26-week randomized treatment period through the date of the last LCIG infusion during the extension period.
Device After	From the first day after the last LCIG infusion through the date of the final device removal (Note: Subjects who have their last infusion on the same date as their final device removal will progress directly from the Open in Randomized Treatment Period/Open in Extension Period to the Off epoch).
Off	Time period after final device removal for subjects who are discontinuing LCIG treatment. Time period after end of study (date of last visit) for all other subjects.

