For subjects randomized to the LCIG group, the date and time of the earliest LCIG tube placement (NJ or PEG-J) recorded on the Device Information eCRF will be considered

the treatment start reference date (REFDT1) and time (DMREFTM). The date of the last LCIG tube removal, or the date of the last LCIG infusion if there is no device removal in the 26-week randomized period will be considered as end of the LCIG 26-week randomized treatment period and the following day will be the post-treatment start reference date (REFEDT1). For LCIG subjects who enter the Extension Period, treatment start reference date in extension period (REFDT2) equals REFEDT1. The date of the last LCIG tube removal or the date the last LCIG infusion if there is no device removal, will be the post-treatment reference date (REFEDT2) of Extension Period.

For subjects in the OMT group, the date after randomization will be considered the treatment start reference date (REFDT1). The date of the final visit during 26-week randomized period will be considered the end of the OMT treatment period and the following day will be the post-treatment start reference date (REFEDT1). For OMT subjects who enter the Extension Period, the date of earliest LCIG tube placement (NJ or PEG-J) recorded on the Device Information eCRF will be considered the treatment start reference date (REFDT2) in Extension period. The date of the last LCIG tube removal, or the date the last LCIG infusion if there is no device removal, will be considered the end of the Extension Period and the following day will be the post-treatment start reference date (REFEDT2).

Study Days during 26-week randomized treatment period will be calculated based on the treatment start reference date (REFDT1). For time points before REFDT1, the Study Day = time point – REFDT1. For time points on or after REFDT1, the Study Day = time point – REFDT1 + 1. Thus, the Study Day is a negative value when the time point of interest is prior to REFDT1 and the Study Day is a positive value when the time point of interest is on or after REFDT1. There is no Study Day 0. The Study Day will be labeled as Rx Day on the data listings. Study Days during Extension Period will be calculated based on the Extension Period start reference date (REFDT2) with the same rule as in 26-week randomized treatment period. For OMT subjects who enter the Extension Period, the study day of Pre in Extension Period will be calculated based on REFDT2.

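### SAP 8.1 makes extension-period PEG-J exposure one day too long for each continuing LCIG subject, because the `+ 1` counts a day that already belongs to the randomized period

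*SAP*

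**What the plan says.** SAP 8.1 defines PEG-J exposure separately for the two periods.

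- **Randomized period, tube not removed after the last infusion** (the case of a continuing LCIG subject): "the duration of PEG-J exposure during the 26-Week Randomized Treatment Period for each subject will be calculated as the date of their final participation", taken as the last contact or visit "during the 26-Week Randomized Treatment Period minus the date of their initial PEG-J placement + 1".
- **Extension, continuing LCIG subjects, tube later removed:** the removal date, less the date of the subject's last "participation in Study M12-927 (last contact or visit date) during the 26-Week Randomized Treatment Period + 1".
- **Extension, continuing LCIG subjects, tube not removed:** the same subtraction and the same `+ 1`, with final study participation in place of the removal date.
- **Extension, OMT subjects:** end date minus their own initial PEG-J placement, plus 1.
- **Extension, LCIG infusion exposure:** the last extension dose date "minus the date of the last dose of LCIG study drug during the 26-week randomized treatment period", with nothing added.

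SAP 6.2 sets the period boundary for LCIG subjects. The extension epoch runs "from the date after the last LCIG infusion during the 26-week randomized treatment period through the date of the last LCIG infusion during the extension". The "treatment start reference date in extension period (REFDT2) equals REFEDT1", and REFEDT1 is the day after the randomized treatment period ends.

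**The concern.** Adding 1 to a difference of dates is right when both end dates belong to the interval and neither has been counted before. That is so for the randomized-period formula and for the OMT extension formulas. It is not so for continuing LCIG subjects, whose extension interval opens on a date that closes the randomized interval.

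The SAP handles the same boundary correctly for infusion exposure, so the PEG-J formulas look like a slip and not a chosen convention. What is at stake is the accuracy of a reported duration. A programmer who follows the text literally will produce the extra day, and a second programmer working from the same text will reproduce it.

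**Working it through.** The SAP states no figure for this quantity, so there is none to reproduce. The check is date arithmetic on its formulas.

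**Inputs**
- P = initial PEG-J placement (SAP 8.1)
- V = last contact or visit in the 26-week period (SAP 8.1)
- R = final PEG-J removal, or final study participation if the tube stays in (SAP 8.1)
- 365.25 days per year (SAP 8.1)
- 44 planned LCIG subjects (Protocol synopsis); the number continuing is not given

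**PEG-J as written**
- Randomized period: V − P + 1, which counts days P to V.
- Extension: R − V + 1, which counts days V to R.
- Sum: (V − P + 1) + (R − V + 1) = R − P + 2.
- Inclusive total from P to R: R − P + 1.
- Excess: 1 day, whatever the dates.

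**The extension figure alone.** If a subject's participation ends on V, so that R = V, the formula gives V − V + 1 = 1 day of extension exposure when there were no extension days. The extra day is therefore present even if the two periods are never added.

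**Control: infusion exposure.** Let F be the first dose, L the last randomized-period dose and E the last extension dose. Then (L − F + 1) + (E − L) = E − F + 1, an excess of 0.

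**Without the `+ 1`.** (V − P + 1) + (R − V) = R − P + 1, an excess of 0.

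**Example with assumed dates** (V = P + 181, R = V + 168)

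| | Randomized | Extension | Sum | Inclusive total |
|---|---|---|---|---|
| As written | 182 | 169 | 351 | 350 |
| Without `+ 1` | 182 | 168 | 350 | 350 |

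A numerical check on 10,000 random sets of dates gave an excess of exactly 1 day every time as written, and 0 without the `+ 1`.

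**Size**
- Per subject: 1/168 = 0.6% of the assumed extension, and 1/350 = 0.3% of the assumed total.
- In subject-years, over an assumed range of continuing subjects: 10/365.25 = 0.03; 20/365.25 = 0.05; 44/365.25 = 0.12 (ceiling).

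**The case against.** The strongest reply is that each formula is a valid inclusive count on its own and that the SAP specifies no analysis adding the two periods. The subject-years sentence in SAP 8.1 sums across subjects, not across periods, and stands under the randomized-period heading. This stands in part: the double count itself appears only in a combined total, which the plan does not request. It does not rescue the extension duration, which is one day long by itself once the extension starts after V.

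A second reply is that the text might mean subtracting the day after V. That would give R − V − 1, one day short, and would require reading the same wording differently from the randomized-period formula, where it plainly means the difference plus one. Neither reading gives R − V.

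A third reply is that SAP 6.2 sets its boundary by last infusion (when no tube is removed), while the PEG-J formulas use last contact or visit, so the two need not fall on the same date. That is so, but the overlap does not depend on it: the randomized-period PEG-J formula itself assigns V to the randomized period.

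A reader might go further and infer that a device-safety rate has an inflated denominator. The documents do not support that. SAP 10.2 reports adverse events, including the GI and GI-procedure events of special interest, as numbers and percentages of subjects, and specifies no exposure-adjusted rate. The Kaplan-Meier analysis of first tube replacement in SAP 8.8 censors on calendar dates and does not use these durations. The duration categories in SAP 8.1 apply to infusion exposure and OMT participation, not to PEG-J.

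Nor is every difference between PEG-J and infusion exposure an error. Device time ends at removal or last contact and drug time at the last dose, so the two would still differ after correction. Only the `+ 1` is at issue.

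**Conclusion.** The point holds as an error in a stated rule with a very small effect. Both extension PEG-J formulas for continuing LCIG subjects give a duration one day too long, and any sum over the two periods would count day V twice.

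This rests on two readings that the SAP supports: the 1 is added to the difference, and day V belongs to the randomized period. The number of continuing LCIG subjects is unknown. The ceiling of about 0.12 subject-years assumes that all 44 planned subjects continue. SAP 4.2 limits the Extension Period to the United States and South Korea, in a study of approximately 10 countries, so the true figure is probably far smaller. If the formulas are also meant for subjects elsewhere who await commercial product, the number is still not given and the ceiling is the same.

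Only a descriptive exposure summary is affected. The efficacy analyses, significance level, power, adverse event incidence and treatment-emergent windows are untouched.

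**What to change.** In SAP 8.1, extension section, delete `+ 1` from the two PEG-J formulas for continuing LCIG subjects (tube removed and tube not removed), so that each becomes the end date minus V. Starting the interval on the day after V and keeping the `+ 1` gives the same result. Leave the OMT formulas as they are, because their interval starts at the subject's own initial placement. The change is two small text edits, with matching lines in the derived-dataset specification and program if already written. It needs no new data and alters no other analysis.

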8.2 OMT Daily Prescribed Dose

Those subjects randomized to OMT, will continue on their current anti-PD medication regimen for the duration of the 26-week randomized treatment period. All anti-PD medications should remain stable for the duration of the study unless adjustments are needed if medically justified. The PI will provide the prescription for continued OMT. Use of medications to treat sleep disorders on an, as needed basis, are prohibited.

8.3 Duration of NJ Period

Duration of NJ Period for each subject who undergoes the optional NJ period will be calculated as the date of NJ removal minus the first NJ infusion date + 1. The first NJ infusion date will be recorded on the Study Drug Administration eCRF. The number and percentage of subjects with each specific number of days will be summarized. In addition, the duration of NJ Period in days will be summarized with descriptive statistics (number of non-missing observations, mean, standard deviation, median, minimum and maximum duration).

8.4 Duration of Initial LCIG Titration Following PEG-J Placement

Duration of initial LCIG titration for each subject will be calculated as the date of the first optimized prescription following PEG-J placement minus the first LCIG infusion date via PEG-J + 1. The first LCIG infusion date will be recorded on the Study Drug Administration eCRF. The current LCIG pump settings at the conclusion of each clinic visit will be recorded on the Study Drug Prescription eCRF. The first set of pump settings that remains unchanged for at least 7 days will be considered the first optimized prescription. The number and percentage of subjects with each specific number of titration days will be summarized. In addition, the duration of initial titration in days will be summarized with descriptive statistics (number of non-missing observations, mean, standard deviation, median, minimum and maximum duration).

8.5 LCIG Daily Prescribed Dose

Each subject's LCIG dose will be individually titrated by adjustment of the LCIG pump settings for the morning dose (mL), continuous flow rate (mL/hr) and extra dose amount (mL). The initial LCIG pump settings and the LCIG pump settings at the conclusion of each clinic visit will be recorded on the Study Drug Prescription eCRF. Subjects are to administer LCIG over a full 16-hour period each day beginning with a morning dose. Extra doses are to be administered only if needed. The daily prescribed dose will be calculated as the morning dose plus 16 times the continuous flow rate. The daily prescribed dose will be summarized in milligrams (mg) of levodopa using the conversion factor of 1 mL LCIG = 20 mg levodopa.

The daily prescribed dose will be summarized with descriptive statistics (number of subjects with non-missing observations, mean, standard deviation, median, minimum and maximum values) for the following.

- Initial LCIG prescription
- First optimized prescription following PEG-J placement
- Final prescription

Descriptive statistics will also be presented for the change in the daily prescribed dose from initial LCIG prescription to first optimized prescription following PEG-J placement and to final prescription and from first optimized prescription to final prescription.

8.6 Total Daily Levodopa Dose

For all randomized subjects, the total daily levodopa dose on the day prior to Visit 1 and on the day of randomization will be considered the subject's screening and baseline levodopa dose, respectively. Following Screening Visit 3, subjects randomized to the LCIG group will have NJ/PEG-J placement and discontinue all anti-PD medications other than levodopa-carbidopa that will be continued during LCIG treatment as post-infusion nighttime therapy. Subjects in the LCIG group are to record all LCIG infusions during the 3 days before each scheduled study visit on a Subject Dosing Diary. Subjects in the OMT group are to record all anti-parkinsonian medications taken during the 26-treatment period on the Subject Dosing Diary.

For each Subject Dosing Diary, the overall total daily dose of levodopa will be determined for each subject in the Safety Dataset, as well as the total for each dosing source for each subject in the LCIG group: LCIG morning dose, LCIG continuous infusion, LCIG extra dose, and LCIG overall. Each subject's average daily dose at each visit, overall and by dosing source, will be calculated by summing the total dose on each Subject Dosing Diary assigned to the visit and dividing by the number of diaries recorded. For LCIG subjects, only diaries reporting at least 12.8 hours of pump operation and only diaries after the initial LCIG titration will be included in this calculation.

For each scheduled visit the mean daily levodopa dose will be summarized, overall and by dosing source, with descriptive statistics (number of subjects with observations, mean, standard deviation, median, minimum and maximum values). The summaries for LCIG extra dose should only include the subjects who dosed in this manner at the visit.

For each scheduled visit during the Extension Period, the mean daily levodopa dose will be summarized, overall and by dosing source, with descriptive statistics (number of

subjects with observations, mean, standard deviation, median, minimum and maximum values) will also be provided for OMT/LCIG subjects who enter the Extension Period.

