While the subject is in the hospital, the study staff may use the Dose Titration Diary as a tool to achieve dose optimization. In the event it is used it should be completed hourly until the dose is optimized and then once AM and once PM it will be completed until the subject is discharged. All adjustments can be recorded on the Dose Titration Diary allowing the Investigator to appropriately adjust, if needed, the following day's morning dose, continuous infusion rate and extra dose until the subject is optimized.

The subject's pump settings for the first infusion of LCIG, the pump settings at the conclusion of each calendar day are to be recorded on the appropriate eCRF.

Following the initial titration period, the site should record the subject's pump settings (morning dose in mL, continuous infusion rate in mL/hr, and lock level) at the conclusion of each clinic visit on the study drug prescription record.

Subject Dosing Diary (LCIG and OMT Groups)

The subject dosing diary should be completed during the 72-hour period (3 days) prior to each clinic visit, as indicated in [Table 3](#). Subjects should be reminded with a phone call prior to each visit to complete the Subject Dosing Diaries and to reinforce the importance of Subject Dosing Diary completion.

Subjects in the LCIG group will record the date and actual clock time of the LCIG pump start and pump stop as well as LCIG extra doses in the diary. In addition, the subject will be instructed to record all oral levodopa-carbidopa taken on the Subject Dosing Diary days.

Subjects in the OMT group will record all anti-parkinsonian medications taken on the Subject Dosing Diary days in the diary.

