During treatment, pump alarms may indicate kinking or knotting of the tube. Additionally there may be a sudden deterioration in treatment response with recurring motor fluctuations due to the distal part of the tube becoming displaced from the upper intestine into the stomach. The location of the tube should be determined radiographically. If necessary, the end of the tube can be repositioned to the proximal small intestine and the new placement confirmed radiographically.

If a problem develops with the LCIG system and the LCIG infusion needs to be temporarily discontinued, the Investigator should then place the subject on a regimen of oral levodopa-IR tablets until the problem is resolved and the LCIG infusion can be resumed the following morning. If the subject is placed on an oral regimen of levodopa IR tablets; the dose prescribed should be based on the dose the subject was receiving just prior to the LCIG infusion interruption and adjust the dose as clinically indicated to stabilize the subject.

Extra LCIG Doses

During initial titration, extra doses may be administered on an hourly basis at the Investigator's discretion based on the subject's response. Subsequently, subjects will be allowed to self-administer additional extra doses of LCIG (at intervals of no less than 2 hours) to address immediate medical needs, such as the rapid deterioration of motor function. Extra doses may be given as required if the subject becomes hypokinetic during the day. If the need for extra doses exceeds 5 times per day, the subject should be instructed to contact the Investigator. The Investigator should then consider the need to increase the subject's continuous daily maintenance infusion dose. After the initial dose setting, fine adjustments of the morning dose, the maintenance dose and extra doses can be made as needed.

Nasojejunal Tube

LCIG is intended for continuous intestinal administration. A temporary nasojejun tube may be used initially with the infusion pump to determine if the subject responds favorably to this method of treatment and to optimize the dose of LCIG before treatment with a permanent PEG-J tube is started. Only the NJ sets available through this clinical study should be used with LCIG. The NJ should be inserted by a gastroenterologist proceduralist, surgeon or interventional radiologist. NJ may also be inserted by the passive method.

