5.5.7 Drug Accountability

Initial study supplies and 6 weeks of LCIG cassettes will be supplied to the Investigator by the drug depot. It is at the discretion of AbbVie and/or the Investigator to discontinue subjects from the study who fail to take and/or return the appropriate amount of study drug.

Treatment regimen compliance will be also be assessed by the Subject Dosing Diary.

LCIG therapeutic systems are received intact and in the correct amounts. This will be documented by the Investigator signing and dating the Proof of Receipt (POR) after he/she receives LCIG from the depot for the initial supplies, and by signing the POR upon receipt of LCIG from the depot. A current (running) and accurate inventory will be kept by the Investigator or the designated representatives in the IRT system, and will include shipping invoices and the date on which study drug was dispensed to the subject. The IRT must be contacted when any subject discontinues the study. The IRT will maintain a current and accurate inventory of all LCIG supplies, accountability, reconciliation, and returns for each site. The investigational site and depot will also maintain current and accurate documentation of study drug details (i.e., kit number, number of used and unused cassettes) in the source document for each subject. Returned study drug cassettes will be retained by the depot until returned for destruction.

An overall accountability of LCIG will be performed and verified by the Sponsor and the depot throughout the study. All original LCIG cassettes (empty or containing unused LCIG) will be returned to the depot, according to instructions from AbbVie and according to local regulations. Labels must remain attached to the containers.

Non-investigational medicinal product (standard of care) (e.g., generic name or brand name) must be obtained commercially.

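### SAP 8.6 averages the LCIG arm's daily levodopa dose only over diaries with at least 12.8 h of pump use, so days of substantial interruption drop out of the only planned summary of dose actually taken

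*SAP*

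**What the plan says.** SAP 8.6 (Total Daily Levodopa Dose) builds each subject's average daily dose at a visit from the Subject Dosing Diaries assigned to that visit. The LCIG arm carries a restriction: "only diaries reporting at least 12.8 hours of pump operation and only diaries after the initial LCIG titration will be included in this calculation". No such condition is set for OMT subjects. The average is the summed dose obtained by "dividing by the number of diaries recorded".

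Two levels of total are named. First, "the overall total daily dose of levodopa will be determined for each subject in the Safety Dataset". Second, for the LCIG arm, there are totals by source: "LCIG morning dose, LCIG continuous infusion, LCIG extra dose, and LCIG overall". None of these sources is oral. SAP 8.6 describes the LCIG diary as a record of infusions over the three days before each visit.

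The protocol collects more than that. Under Subject Dosing Diary in section 5.3.1.1, "the subject will be instructed to record all oral levodopa-carbidopa taken on the Subject Dosing Diary days". It foresees oral levodopa in this arm in three settings: rescue (5.2.3.3), night-time use after the infusion stops (5.2.3.4), and interruption of the LCIG system, when "the Investigator should then place the subject on a regimen of oral levodopa-IR tablets until the problem is resolved" (5.5.1.2). The diary is also a compliance measure: "Treatment regimen compliance will be also be assessed by the Subject Dosing Diary" (5.5.7).

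The planned infusion day is set in SAP 8.5: "Subjects are to administer LCIG over a full 16-hour period each day beginning with a morning dose". SAP 8.5 summarises prescribed dose, not dose taken.

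**The concern.** The filter selects diary days on pump time, which largely determines the dose being reported. A day lost to a blocked or displaced tube, a pump fault, intolerance or poor use gives a low LCIG dose, and such a day is removed before averaging. A subject whose diaries at a visit are all short contributes nothing at that visit. OMT diaries are averaged whatever was taken, so the two arms' dose figures are not built the same way.

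At stake is the description of exposure. In an open-label comparison of routes of levodopa delivery, readers will want to know how much levodopa each arm took and by which route. The days removed include those on which the protocol expects oral levodopa to replace the infusion. Two gaps in wording add to this. The denominator is not reconciled with the filter, and the content of the overall total is not stated.

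**Working it through.** **Cutoff.** The SAP gives no derivation for 12.8 h. Against the 16 h day in SAP 8.5, 12.8 / 16 = 0.80. Days below 80% of planned pump time go; days from 12.8 h upward stay.

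**Inputs for the illustration.**
- Conversion: 20 mg levodopa per mL (SAP 8.5).
- Morning dose 7.5 mL and rate 4 mL/h, the midpoints of the usual ranges of 5 to 10 mL and 2 to 6 mL/h (Protocol 5.5.1.2).
- Three diaries per visit (Protocol 5.3.1.1; SAP 8.6).
- Assumed: two full days and one short day at the same settings, with no extra doses. The documents give no frequency for short days.

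**Formula.** Daily LCIG dose in mg = 20 × (morning mL + rate × hours).
- Full day: 20 × (7.5 + 4 × 16) = 1430 mg.
- 8 h day: 20 × (7.5 + 4 × 8) = 790 mg.
- Retained day at the cutoff: 20 × (7.5 + 4 × 12.8) = 1174 mg, and 1174 / 1430 = 82% of a full day.

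**Three ways to average the same visit, with one 8 h day.**
- All diaries: (1430 + 1430 + 790) / 3 = 1217 mg.
- Filter applied to both sum and denominator: (1430 + 1430) / 2 = 1430 mg. The ratio 1430 / 1216.7 = 1.175, so 17.5% too high.
- Filter applied to the sum, but divided by all three recorded diaries: (1430 + 1430) / 3 = 953 mg. The ratio 953.3 / 1216.7 = 0.784, so about 22% too low.

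**How the size depends on the short day** (filter applied to both sum and denominator, one short day in three).

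| Pump hours on short day | Dose that day (mg) | Mean, all diaries (mg) | Filtered mean (mg) | Overstatement |
|---|---|---|---|---|
| 12.7 | 1166 | 1342 | 1430 | 6.6% |
| 8 | 790 | 1217 | 1430 | 17.5% |
| 4 | 470 | 1110 | 1430 | 28.8% |
| 0 (no morning dose) | 0 | 953 | 1430 | 50.0% |

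The settings matter little. For one 8 h day, 5 mL with 2 mL/h gives 740 against 633 mg (16.8%), and 10 mL with 6 mL/h gives 2120 against 1800 mg (17.8%). With no short days, the filter changes nothing.

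These figures concern LCIG-delivered levodopa. If the overall total includes oral levodopa, the effect on that total also depends on how much was taken by mouth on the short day, for which the documents give no figure.

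**The case against.** The case on the other side is substantial and limits the point in five ways.

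- **Oral levodopa.** A reader might infer that the SAP leaves oral levodopa out of the LCIG arm's total. The text does not support that. The overall levodopa total is named separately from the LCIG overall line; if it held only LCIG, the two would duplicate each other in that arm. It may well include oral levodopa. What stands is that the SAP does not say so and plans no oral source line.
- **Rescue days.** A reader might infer that the filter hides rescue use. It acts on pump hours, not on rescue. Protocol 5.2.3.3 provides for rescue tablets during the scheduled infusion, so rescue on a day of 12.8 h or more stays in. Only rescue on short days is lost.
- **Other outputs.** SAP 8.7 summarises pump hours at each visit, including the minimum, with no stated filter. SAP 8.8 tabulates tube replacements. SAP 7.4 tabulates medications taken. Interruptions and oral use are therefore not invisible. But 8.7 draws on start and end times from the clinic-visit prescription eCRF, 8.8 carries no dose, and 7.4 gives use without dose, with levodopa-carbidopa left out of its count of motor-symptom medications. None of them counts short diary days.
- **Importance.** The table is descriptive. No between-arm test of dose and no adherence rate is planned from it, and compliance is also judged from cassette use (Protocol 5.5.6). A reader might infer that the filter obscures how much of the Week 26 effect came with added oral levodopa; no dose table could apportion that effect.
- **Magnitude.** The percentages come from an assumed scenario and from one reading of the denominator.

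The objection does not remove the selection rule itself, its absence from the OMT arm, or the unsettled denominator.

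**Conclusion.** The point holds as a reporting weakness in SAP 8.6. The only planned summary of levodopa dose actually taken is, for the LCIG arm, conditioned on at least 80% of planned pump time, and its LCIG mean is biased upward whenever short days occur. With one short diary day in three, the overstatement runs from about 7% (a day just under the cutoff) to 50% (no infusion), and it is zero if no day is short. This assumes unchanged pump settings and that excluded diaries also leave the denominator. If they stay in the denominator, the 8 h example turns into an understatement, so identical data could be reported as 1430 mg or 953 mg.

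Neither primary endpoint uses this average. The 1250 mg levodopa subgroup in SAP 9.6 would be touched only if its LCIG value came from these filtered diaries, which the SAP does not say.

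**What to change.** In SAP 8.6:

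- Compute the average daily dose over all post-titration diaries, with those same diaries as the denominator. Keep the version restricted to 12.8 h or more as a supplementary table.
- Report the number and percentage of diary days below 12.8 h, and of subjects with any such day.
- State that the overall total includes oral levodopa, and list oral night-time and oral rescue levodopa as separate sources for the LCIG arm.

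The protocol already has the diary collect the data needed. The cost is a few sentences and one or two extra descriptive tables. The downside is that LCIG delivery may look less complete than under the present rule. No confirmatory test changes.
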